		Annex
At least two prior	-Descriptive	Where the BNT162b2 XBB.1.5 vaccine is the
doses of mRNA	-Subgroup	exposure of interest. Using all-available
vaccine and no		lookback data, received at least two prior
bivalent BA.4/5		doses of mRNA vaccine (regardless of
COVID-19		formulation or brand) and did not receive
vaccine		bivalent BA.4/5 COVID-19 vaccine.
		Note: the doses must be at least 21 days apart.
		Yes or No
		The list of codes is provided in the Protocol Annex
Never COVID-19	-Descriptive	Using all-available lookback data, no prior
vaccinated	-Subgroup	receipt of a COVID-19 vaccine (regardless of
		formulation)
		Yes or No
		The list of codes is provided in the Protocol
		Annex
Time since last	-Descriptive	Using all-available lookback data, time in
COVID-19	-Subgroup	months between index date and prior receipt
vaccine		of a COVID-19 vaccine (regardless of
		formulation)
		The list of codes is provided in the Protocol
		Annex
Predominant	Time-varying	Using a time-varying covariate, to indicate
variant	covariate, to produce	whether an event happened in the XBB era
	stratified analyses	(September 11, 2023 – January 5, 2024) or
		JN1 era (January 6, 2024 – end of data
		collection [March 11, 2024])

5.4. Data sources

The sources of the data are the State of California and the State of Louisiana vaccine registries linked to closed claims in HealthVerity.

5.4.1. California and Louisiana Immunization Registries

The California Immunization Registry is run by the California Department of Public Health and collects nearly all records of COVID-19 vaccinations administered in the state of California.

Data include a unique HealthVerity person identification code, vaccination event date and Clinical Vaccines Administered (CVX) code. CVX codes are unique to brand and formulation of vaccine.

Data is linked using HealthVerity's tokenization software, whereby specific patient identifiers are passed through the software and a de-identified patient ID is assigned. The same tokenization process is applied to closed claims sourced by HealthVerity, and patients can thus be linked across data sources. The tokenization process occurs outside of Pfizer, no personal identifying information will be transferred, and Pfizer will only have access to de-identified data. The data comply with Health Insurance Portability and Accountability Act (HIPAA) regulations.

The Louisiana Vaccine Registry is structured and accessed in the same way as California.

5.4.2. HealthVerity's Administrative Claims Data

HealthVerity closed claims will be limited to approximately 19 million patients residing in California and approximately 3.8 million in Louisiana.

HealthVerity's description of their data is that they are generally representative of the age and sex distribution of the population. For our specific research context, samples created from HealthVerity claims also generally follow California's demographic patterns with respect to age & sex.

The California subset of HealthVerity does not include patients in the Kaiser Permanente network. Insurers contributing to closed claims in both states include a mix of commercial payers, Medicare Advantage/Part C pains, and Medicaid Managed Care plans. Data elements include patient demographic information, inpatient/outpatient visit-level information such as diagnoses, procedures, and length of stay, hospital characteristics, and medication information. Owing to the nature of claims, the data represent the final set of diagnoses over the course of the hospitalization sent to the patient's insurer for reimbursement, with diagnosis prioritization assigned by clinicians or hospital staff. For inpatient encounters, the data will be assumed to represent the overarching events during hospitalization and may be less subject to rule out diagnosis codes than electronic health record data.

Death information is available and is sourced from over 40,000 public and private sources nationally. The coverage rate, estimated at over 90% of CDC reported deaths through present day, is based on the number of deaths in the Fact of Death Mortality Index compared to the number of deaths reported by the CDC. Due to HIPAA privacy restrictions, date of death is reported as month and year. Cause of death is not available.

5.5. Sample Size and Power Calculations

Since the current study utilizes retrospective deidentified data without ability to recruit to a target, sample size calculations are not applicable. Further, this is a descriptive study without a priori specified hypotheses. However, we examined the precision of the expected XBB.1.5 absolute VE estimates for the outcomes under various scenarios.

Assuming uptake similar to that seen with the BA.4/5 vaccine, and non-differential uptake by age groups, we could anticipate in California:

(75% of 12 million are adult)*(16% uptake)*(60% of doses were Pfizer-BioNTech)

~ 864,000 adult XBB doses in California

Among these 9 million adults, 95% were assumed to be non-immunocompromised and used as the sample size at start of follow-up. Assuming similar absolute VEs to those seen with the BA.4/5 vaccine for symptomatic COVID-19 infections, we could anticipate estimates between 20 and 40%. To assess the precision for a range of outcomes, incidence rates of 50, 100, 1000 and 10,000 cases per 100,000 unvaccinated persons during the study period were considered. A censoring rate of 5% by the end of the study period was used. A uniform vaccination rate between 14 days after study index and the end of follow-up was assumed.

Survival and censoring times were simulated assuming exponential distributions. Vaccination status was modelled as a time-varying covariate. Hazard ratios were input as 1-(VE/100). Simulations were run a minimum of 10 times per scenario. Cox regression models were run on each simulated dataset to estimate the 95% CIs for the log HRs. Means were generated and exponentiated to obtain the 95% CIs for the VEs using (1- HR) x 100 and used to describe VE precision. Simulations were repeated on 25% of the initial sample size to represent the precision in a potential subgroup.

Table 5.4 Simulated 95% Confidence Intervals [Total Number of Events] for BNT162b2 XBB.1.5 Vaccine Effectiveness Estimates

Number at Start of	Vaccine Effectiveness,	Cases per 1	00,000 Unvacci Stu		s by End of
Follow-up	%	50	100	1000	10,000
8,550,000	20	7, 29 [4116]	12, 27 [8242]	18, 23 [81,702]	19, 21 [782,794]
	30	20, 40	22, 36	28, 32	29, 31
	40	[4104] 30, 49	[8144]	[81,108] 38, 42	[777,275] 39, 41
		[4019]	[8095]	[80,490]	[771,141]
2,137,500	20	-3, 39 [1026]	4, 34 [2072]	15, 24 [20,348]	18, 21 [195,697]
	30	10, 49 [1022]	14, 42 [2042]	25, 34 [20,297]	28, 31 [194,371]
	40	20, 57 [1016]	27, 52 [2022]	36, 44 [20,104]	39, 41 [192,827]

Table 5.4 shows that there should be sufficient sample size in the California registry to produce 95% CIs for VEs that exclude 0 for the evaluated VEs and incidence rates, except for the rare event scenario in a subgroup. Assuming similar VEs in the two state registries, the inclusion of patients from the Louisiana registry would increase the precision further.

5.6. Missing Data

No imputation for missing values will be performed. Subject to patient counts (Section 5.7.2), missing or 'unknown' values will be reported and analyzed as separate categories and included in the totals.

5.7. Statistical Methodology and Analyses

5.7.1. General Considerations

Descriptive statistics will be used to summarize variables. For categorical variables, the frequency and percentage of patients in each category will be presented. Percentages will be based on the total number of relevant patients. For continuous variables, data will be presented as means, standard deviations, medians, 25th and 75th percentiles, minimums and maximums. Continuous variables may be additionally categorized and analyzed as categorical variables.

No statistical hypotheses are specified and there will be no correction for multiple comparisons.

Time in days between two dates will be calculated as (date2 - date1) + 1, where date2 is on or after date1. Where date2 is before date1, time in days between two dates will be calculated as (date2 - date1). Index date will be considered as Day 1. There is no Day 0.

Unless stated otherwise, one year is defined as 365 days, and one month is defined as 30 days.

All data analysis will be conducted using statistical software SAS version 9.4 or R version 4.1.0 or later.

5.7.2. Minimum Sample Size Requirements

In order to maintain patient de-identification, outcomes, covariates and subgroups will have at least 10 patients in each category to be included in the analysis.

In addition, a minimum of five events per variable (the number of degrees of freedom) will be required in each level of the outcome variable in the adjusted Cox regression models to minimize the potential for biased estimates.⁶ Note, as an example, a categorical predictor variable with three levels contributes two degrees of freedom.

5.7.3. Index Date, Baseline and Follow-up

The index date for each individual will be defined as the BNT162b2 EUA or FDA approval date (Table 5.1). Age and sex will be assessed at index date. The baseline period used to assess other patient characteristics are specified for each covariate in Table 5.3.

Unvaccinated follow-up time will occur from the date of FDA authorization/approval until 13 days after the receipt of vaccination, the outcome of interest, or are censored at the first of the following: 6 months of follow-up, end of medical and/or pharmacy enrollment, receipt of a non-Pfizer BioNTech vaccine. Where mortality is not the outcome of interest, follow-up time will be additionally censored at death. Where mortality is the outcome of interest, follow-up time will be additionally censored at a death not meeting the outcome criteria.

Vaccinated follow-up time will occur from 14 days after the receipt of vaccination until the outcome of interest, or are censored at the first of the following: 6 months of total follow-up (ie, 11 March 2024), end of medical and/or pharmacy enrollment, receipt of a non-Pfizer BioNTech vaccine or receipt of a second BNT162b2 COVID-19 vaccine dose. Where mortality is not the outcome of interest, follow-up time will be additionally censored at death. Where mortality is the outcome of interest, follow-up time will be additionally censored at a death not meeting the outcome criteria.

5.7.4. Eligibility, Demographic, Clinical and Exposure Characteristics

The number and percentage of patients meeting the eligibility criteria will be reported in a subject evaluation table.

Descriptive statistics will be used to summarize patient demographics, clinical characteristics, and healthcare utilization on or prior to index date. Descriptive statistics will be repeated by BNT162b2 vaccination status by the end of follow-up. Standardized mean differences (SMD) will be used to assess covariate balance by BNT162b2 vaccination status by the end of each month of follow-up. Overall SMDs will be presented for each covariate as the maximum absolute value across the months. SMDs \leq 0.1 will be considered as evidence of negligible imbalance.

Summaries of the overall follow-up time in months will be presented and calculated as time from index date to the earliest of 6 months of follow-up, end of medical and/or pharmacy enrollment, receipt of a non-Pfizer BioNTech COVID vaccine, receipt of a second BNT162b2 COVID-19 vaccine dose or death.

The number of patients who are BNT162b2 vaccinated by the end of the overall follow-up will be reported. Kaplan-Meier analysis will be used to summarize the percentage of persons who are BNT162b2 vaccinated by the end of each month of follow-up. Patients will be censored at the earliest of the following: 6 months of follow-up, end of medical and/or pharmacy enrollment, receipt of a non-Pfizer BioNTech COVID-19 vaccine or death.

The above analysis will be repeated by age group and state of residence.

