8.5. Study Size

Since the current study utilizes retrospective deidentified data without ability to recruit to a target, sample size calculations are not applicable. Further, this is a descriptive study without *a priori* specified hypotheses.

Initial data feasibility work has revealed approximately 19 million persons in the state of California with claims available in HealthVerity, among which approximately 25% are pediatric and 75% adult. Among these, approximately 12 million have at least one year of continuous medical and pharmacy enrollment. By end of 2023, we expect to have finished contracting to add approximately 565,000 additional persons. The proportion of these additional persons who will have 1-year continuous enrollment, and therefore the sample size estimates below have taken the conservative approach to not yet include these people.

We have identified 63% of persons in the claims data have at least one COVID-19 vaccine, and 16% received at least one bivalent dose. The claims population we have is not a random sample of Californians and may differ from the state's population in systematic ways (e.g. the age distribution). While differences may exist, we have high confidence in our ability to represent vaccination status for the individuals in our claims population.

We expect to begin to see XBB doses in data delivered in November 2023. Assuming uptake similar to that seen with the BA.4/5 vaccine, and non-differential uptake by age groups, we could anticipate in California:

(25% of 12 million are pediatric)*(16% uptake)*(60% of doses were Pfizer-BioNTech)

~ 288,000 pediatric XBB doses in California

(75% of 12 million are adult)*(16% uptake)*(60% of doses were Pfizer-BioNTech)

~ 864,000 adult XBB doses in California

Additional doses will be observed in Louisiana. In order to maintain patient de-identification, outcomes, covariates and subgroups will have at least 10 people in each category for inclusion in outputs. Throughout the protocol, this is referred to as "If sample size allows".

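### Monthly BNT162b2 uptake is to be estimated by Kaplan-Meier with other-brand vaccination and death censored, which slightly overstates the percentage vaccinated

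*SAP*

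**What the plan says.** In section 5.7.4 of the Aim 1 SAP the stated target is a percentage of people: "Kaplan-Meier analysis will be used to summarize the percentage of persons who are BNT162b2 vaccinated by the end of each month of follow-up". The censoring rule follows: "Patients will be censored at the earliest of the following: 6 months of follow-up, end of medical and/or pharmacy enrollment, receipt of a non-Pfizer", and the list ends with "receipt of a non-Pfizer BioNTech COVID-19 vaccine or death". The results are then broken down: "The above analysis will be repeated by age group and state of residence". Section 5.7.4 of the Aim 2 SAP has the same estimator, censoring events and strata for children.

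One companion figure is planned, a count at the end: "The number of patients who are BNT162b2 vaccinated by the end of the overall follow-up will be reported". Neither SAP plans a cumulative incidence estimate.

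The only uptake figures are planning values. Protocol section 8.5 reports that in the claims data "16% received at least one bivalent dose". Section 5.5 of the Aim 1 SAP carries this forward without any difference by age: "Assuming uptake similar to that seen with the BA.4/5 vaccine, and non-differential uptake by age groups, we could anticipate in California" a number of adult doses given by the product "75% of 12 million are adult)*(16% uptake)*(60% of doses were Pfizer-BioNTech".

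**The concern.** The four censoring events are of two kinds. Disenrollment and the end of the 6-month window only hide whether a person was vaccinated, and censoring is right for them. Death rules out a later dose. An other-brand dose ends, under the plan's own follow-up rules, the period in which the person could be counted as a first BNT162b2 recipient. Kaplan-Meier treats people censored for either reason as if they would still have taken BNT162b2 at the rate of those remaining at risk. The resulting figure answers what uptake would have been had other brands and deaths not existed. That is not the percentage the sentence promises.

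The competing event is not rare relative to the event counted. A 60% share of 16% uptake leaves 6.4% of people taking another brand, against 9.6% taking BNT162b2. The error runs in one direction and does not shrink with sample size. Uptake is not a listed objective, but the protocol's rationale section names it as a use of the linked data, and these figures will be read by age group and by state.

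**Working it through.** **Inputs**

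| Quantity | Value | Source |
|---|---|---|
| Adults with one year of enrollment, California | 75% of 12 million = 9 million | Aim 1 SAP 5.5 |
| Any-brand uptake | 16% | Protocol 8.5; Aim 1 SAP 5.5 |
| BNT162b2 share of doses | 60% | Aim 1 SAP 5.5 |
| Other censoring by end of study | 5% | Aim 1 SAP 5.5 |
| Vaccination timing | uniform over follow-up | Aim 1 SAP 5.5 |
| 6-month mortality | 0%, and 0.5% to 2% | assumption; not in the documents |
| Any-brand uptake above 16% | 30%, 40%, 50% | assumption; not in the documents |

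**Step 1: the plan's own figure.** 0.75 × 12,000,000 × 0.16 × 0.60 = 864,000 doses, as stated. Divided by 9,000,000 adults this is 9.6%. The pediatric product gives the same proportion: 0.25 × 12,000,000 × 0.16 × 0.60 = 288,000, and 288,000 / 3,000,000 = 9.6%.

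**Step 2: formula.** Let F1 be the proportion who take BNT162b2, F2 the proportion who take another brand, D the proportion who die, and T = F1 + F2 + D. If the cause-specific hazards keep a constant ratio over follow-up, the planned estimator converges to

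1 − KM = 1 − (1 − T)^(F1/T),

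while the percentage actually vaccinated is F1, which is what Aalen-Johansen estimates.

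**Step 3: planning values.** F1 = 0.096, F2 = 0.064, D = 0: 1 − 0.84^0.6 = 0.0993. That is 9.93% against 9.60%, an excess of 0.33 points (3.5% relative). On 9 million adults this corresponds to about 30,000 people.

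- With D = 0.005: 1 − 0.835^(0.096/0.165) = 9.96%, excess 0.36.
- With D = 0.02: 1 − 0.82^(0.096/0.18) = 10.04%, excess 0.44.

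The constant-ratio assumption can be bounded. With no deaths, if every other-brand dose preceded every BNT162b2 dose, the figure would be 0.096 / (1 − 0.064) = 10.26%. If all came after, it would be 9.60%.

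**Step 4: assumed higher uptake, same 60:40 split, no deaths.**

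| Any-brand uptake | Actual BNT162b2 | 1 − KM | Excess (points) |
|---|---|---|---|
| 30% | 18.0% | 19.3% | 1.3 |
| 40% | 24.0% | 26.4% | 2.4 |
| 50% | 30.0% | 34.0% | 4.0 |

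**Step 5: month by month.** A simulation of 2,000,000 people with 16% uptake, the 60% share, uniform vaccination times over 182 days, 5% disenrollment and 0.5% deaths gave:

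| Month (30 days) | 1 | 2 | 3 | 4 | 5 | 6 |
|---|---|---|---|---|---|---|
| 1 − KM, % | 1.60 | 3.22 | 4.84 | 6.49 | 8.15 | 9.86 |
| Aalen-Johansen, % | 1.59 | 3.18 | 4.76 | 6.33 | 7.91 | 9.50 |

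Month 6 is day 180 of 182, so Aalen-Johansen reads 9.50% and not 9.60%. The gap is negligible in month 1 and grows with follow-up. The crude count over everyone gave 9.37%, below the true 9.60%, because it ignores disenrollment.

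**Step 6: comparing strata** (illustrative values, no deaths).

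- Same 60:40 split, 16% against 40% any-brand uptake: true difference 24.0 − 9.6 = 14.4 points; by 1 − KM, 26.4 − 9.9 = 16.5. The difference is enlarged.
- 24% BNT162b2 plus 2% other brand (excess 0.27) against 15% plus 10% (excess 0.85): true difference 9.0 points; by 1 − KM, 24.27 − 15.85 = about 8.4. The difference is reduced.

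**The case against.** The strongest reply is that this hardly matters. At the only uptake values in the documents the excess is a third of a point. Even the 16% may be generous for a 6-month window, because it describes a bivalent vaccine authorized from August 2022 and reported in a November 2023 protocol. The curve is a cohort description, and a crude end-of-follow-up count stands beside it. The censoring mirrors the follow-up rules of the VE analysis, and a net probability under those rules is a recognized quantity. All of this stands as a limit on importance. It does not make the figure the percentage of people vaccinated. The crude count is no substitute, because it is not monthly and its simple proportion ignores disenrollment.

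Three stronger readings are tempting, and the documents do not support them.

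- *The overstatement is greatest in high-uptake age groups, and differences between groups are exaggerated.* This needs a similar brand split across strata. The driver is the amount of other-brand vaccination and death in each stratum, and step 6 shows a difference that shrinks. The documents give no uptake, brand share or mortality by age or state, and planning assumes equal uptake across ages.
- *The error is several points.* An excess of 1 point or more appears only at around 30% any-brand uptake and above, which is an assumption.
- *The VE estimates are biased by this.* The Cox models use each person's time-varying exposure and not the Kaplan-Meier percentages. Censoring at other-brand receipt is legitimate for a cause-specific hazard.

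**Conclusion.** The point holds as a small, systematic error in a descriptive output. The direction is certain: with competing events censored, 1 − KM cannot lie below the cumulative incidence, and it lies above whenever an other-brand dose or a death precedes some BNT162b2 doses. At the planning values the month-6 excess is about 0.33 points, or 0.36 to 0.44 points under the assumed mortality. These sizes rest on a constant ratio between the hazards of the two brands and of death. The rows at 30%, 40% and 50% show only how the gap would grow if uptake were that high and the brand split unchanged. For age groups and states the documents settle neither the size of the distortion nor its direction.

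**What to change.** In section 5.7.4 of both the Aim 1 and the Aim 2 SAP, replace the Kaplan-Meier estimate by the Aalen-Johansen cumulative incidence of first BNT162b2 XBB.1.5 vaccination. Treat other-brand COVID-19 vaccination and death as competing events, and only disenrollment and the end of the 6-month follow-up as censoring. Use the same estimator overall, by age group and by state. Showing the other-brand cumulative incidence alongside would let readers see the brand mix that drives the gap.

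If a Kaplan-Meier curve is kept as well, label it a net probability, assuming no other-brand vaccination or death, and do not describe it as the percentage vaccinated.

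The cost is one procedure option and a sentence in each SAP. The reported uptake becomes slightly lower, and no VE analysis changes.

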We will further use incidence of the COVID-19 endpoint in unvaccinated persons and apply VE estimates to estimate the number of cases averted per 100,000 person-months. This estimate of the vaccine-preventable disease incidence will be generated for each endpoint as the adjusted VE as a proportion multiplied by the incidence rate among unvaccinated persons.

The above analysis will be repeated by age group for each outcome, subject to patient counts (Section 5.7.2). Additionally, the analysis for the primary outcome will be repeated by state of residence. Subject to the distribution of time since last prior COVID-19 vaccine, relative VEs may also be repeated by subgroups of that variable.

5.7.6. Assessment of Residual Confounding

Negative control outcomes will be used to quantify residual and unmeasured confounding (Table 5.2). The analysis described above will be conducted for the negative control outcomes. Persons with a diagnosis of the negative control outcome within 90 days prior to index date will be excluded from the analysis for that outcome.

In the event aHR for negative control outcomes have a significant effect (95% CI do not include null value of 1), then the set of confounders will be adjusted to allow for calibration. The COVID-19 related outcome VE results may be additionally reported after correcting for estimates of the bias.⁷

BNT162b2 (COVID-19 vaccine formulations)
C4591065 NON-INTERVENTIONAL STUDY STATISTICAL ANALYSIS PLAN FOR SECONDARY DATA
COLLECTION STUDY
Version 1.0, 16 January 2024

